Device success, which was defined as the ability to successfully deliver and deploy the Tack implant(s) to the intended target sites was successfully achieved in 32/35 (91.4%; 95% CI 77.6, 97.0) subjects. In all three subjects where device success was not achieved, the physician was unable to advance the device to the desired position due to tortuous vessel anatomy and/or torque transmission in the delivery catheter. Procedure Success was defined as demonstrated

vessel patency as reported by the physician (visual estimate) without occurrence of MALE + POD on the date of procedure. Procedure success was achieved in 34/35 (97.1%; 95% CI 85.5, 99.5) subjects in the Safety Sample and 31/32 (96.9%; 95% CI 84.3, 99.5) in the Performance Sample. These data support that the Tack device performed as intended in this subject cohort.

ABI was significantly ( $p < 0.05$ ) improved at all time points. At all post-procedure time points there was a significant ( $p < 0.05$ ) in audible Doppler signal. Specifically, at 12 months, 10/34 lesions improved, 23/34 had no change, and 1/34 was worse.

**Table 5** below summarizes amputation-free survival, survival, freedom from amputation, freedom from clinically driven TVR, and freedom from clinically driven TLR for all subjects. At 12 months, the amputation free-survival rate was 84.5% (95% CI; 66.6, 93.2) and freedom from clinically driven TVR and TLR was 93.5% (95% CI; 76.6, 98.3).

**Table 5. Summary for Amputation-Free Survival, Survival and Freedom from Amputation, Clinically Driven Target Vessel Revascularization and Clinically Driven Target Lesion Revascularization in All Enrolled Patients**

Parameter	30 Days	3 Month	6 Month	12 Month
Amputation-free survival, composite of death/amputation	100%	93.8%	93.8%	84.5%
Survival	100%	97%	97%	97%
Freedom from amputation of the limb (above the ankle)	100%	96.8%	96.8%	87.1%
Freedom from clinically driven target vessel revascularization (TVR)	100%	100%	93.5%	93.5%
Freedom from clinically driven target lesion revascularization (TLR)	100%	100%	93.5%	93.5%

Primary patency was defined post-hoc as presence of a Doppler signal, freedom from clinically driven target lesion revascularization (CD-TLR) and major amputation (above the knee). Primary patency was determined per patient and per vessel. Primary patency is lost at the first occurrence of CD-TLR, major amputation or lack of an audible signal observed at the 1, 3, 6 or 12 month follow-up.

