 Wound assessment is required and all efforts should be made to acquire photographs of the wound to support the assessment for healed, improved, unchanged, worsening, amputated or new (if applicable).

 Both ABI and TBI are required at baseline and throughout follow-up. If during baseline, an ABI or TBI is not attainable, due to non-compressible arteries or prior digital amputation, this shall be noted on the electronic case report form

(eCRF). If ABI, ankle pressure or toe pressure cannot be acquired, TcPO2 may be recorded, if possible, to confirm a Wifi Ischemia Grade.

 Only the following types of adverse events (AEs) shall be recorded in the eCRF: Serious adverse events (SAEs), or any AE that is classified as ‘possibly’ or ‘definitely’ related to the study device and/or study device procedure by the investigator. Assessments of MALE+POD will also be part of the AE assessment.

 Follow-up assessments (required at the 30-day visit and beyond) that cannot be performed due to a subject’s medical condition (i.e., amputation) will not be considered a deviation if it is fully documented in source records.

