and a one-sided Type I error rate of 2.5%, a sample size of 171 subjects provides 90% power to demonstrate that the observed 30-day MALE+POD rate is below the performance goal of 12%.

Since the required sample size for the primary efficacy endpoint (186), is larger than the required sample size for the primary safety endpoint (171), an effective sample size of 186 subjects meeting the ITT definition will be assumed. Assuming approximately 20% loss to follow-up, total enrollment will be  $186/0.80$  or 232 subjects.

The secondary endpoint of primary patency of the tacked segment of the treated lesion at 6 months will also be formally tested against a performance goal of 64%. The performance goal of 64% was chosen as a result of a meta-analysis combining 13 papers that reported 6-month patency for standard PTA or from which the 6-month patency rate could be derived. These papers covered several patient populations, however all these populations are target populations for use of the Tack. A meta-analysis was performed on the results reported in these papers and the random effects estimate of 6-month patency was 63.5%. Therefore, 64% was chosen as the performance goal. Assuming an observed 6-month patency rate of 81% and a one-sided Type I error rate of 2.5%, the effective sample size given above for the primary efficacy endpoint of 175 would provide greater than 90% power to detect the difference between an observed 6-month patency of 81% and the performance goal of 64%.

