### 19.8.3. SECONDARY EFFICACY ENDPOINTS

The secondary efficacy endpoint of 6-month patency will be estimated as the proportion of tacked segments of the lesion(s) that are still patent at 6 months. A one-sided lower 97.5% confidence bound will be calculated for this estimate using the standard normal approximation. This lower bound will be compared to the performance goal of 64%. The hypotheses being tested are:

$$H_0 : P_{\text{Patency}_{6\text{month}}} \leq 64\%$$

$$H_a : P_{\text{Patency}_{6\text{month}}} > 64\%$$

where  $P_{\text{Patency}_{6\text{month}}}$  is the proportion of subjects whose tacked portion of the vessel is still patent 6 months post procedure. Patency will also be displayed using a Kaplan-Meier curve.

The secondary efficacy endpoint of target limb salvage at 6 months will be summarized using the Kaplan-Meier method to estimate freedom from above-ankle target limb amputation. The final 6-month estimate will be presented along with 95% confidence intervals. All subjects that meet the ITT definition are included in this analysis.

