#### 19.11. HANDLING OF MISSING DATA

For the primary analysis, only complete data will be used. Data will be considered “complete” if the subject had the event of interest at or prior to the time point for analysis and/or if the subject’s status is known at any time beyond the analysis window. Subjects without sufficient follow-up based on the lower end of the visit window will be excluded from the analysis (that is, subjects must have at least 28 days of follow-up for the 30 day endpoints, 6 months minus 30 days for the 6 month endpoints and 12 months minus 30 days for endpoints defined at 1 year). Thus, subjects without events but whom are known to be event free at a later visit will have their data imputed backward but not forward for the primary analysis.

As a sensitivity analysis, missing values for the primary endpoints will be replaced by regression imputations based on a multivariate logistic regression analysis of completed cases (those that have follow-up at the required time point or experienced the endpoint in question prior to final follow-up visit). Covariates to consider for inclusion in the logistic regression include but are not limited to: age, sex, history of hypertension, diabetes, previous peripheral vascular intervention, BMI, dissection location (mid popliteal (P2), distal popliteal (P3), tibioperoneal trunk, peroneal, anterior tibial, or posterior tibial), and baseline Rutherford class. Backward selection will be used to identify predictors. In the event there are no significant predictors in the logistic regression model at  $\alpha=0.1$ , a “hot deck” method will be employed where a random selection of the outcome from a group of completed cases with similar baseline characteristics will be used as the imputed value using simple random sampling with replacement. The baseline characteristics to be used for the hot deck method will include but are not limited to age ( $\neq$  median), sex, dissection location (mid popliteal (P2), distal popliteal (P3), tibioperoneal trunk, peroneal, anterior tibial, or posterior tibial), use of statin medication, current smoker status and baseline Rutherford class.

With either method of imputation, five complete datasets will be constructed. Each dataset will be analyzed separately and then combined in an overall analysis across the five complete datasets.

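### The complete-case rule removes an amputated limb with no usable scan from the tested 6-month patency endpoint instead of counting it as a loss

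*Combined protocol and SAP*

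**What the plan says.** Sections 6.2, 19.4 and 24 define tacked-segment patency as flow on duplex ultrasound, or on an angiogram if one falls within the visit window. Loss requires evidence of no flow. The section 24 entry for a duplex no-flow reading also requires flow to be seen in the corresponding vein, so a loss has to come from an actual examination. Amputation is not mentioned.

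Section 19.8.3 says patency is "estimated as the proportion of tacked segments of the lesion(s) that are still patent at 6 months", with a one-sided lower 97.5% normal-approximation bound compared with 64%. Section 19.13 makes this the only secondary endpoint with a formal test, carried out only if both primary endpoints are met.

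Table 8, footnote 12, says that follow-up assessments which cannot be done because of the subject's "medical condition (i.e., amputation) will not be considered a deviation if it is fully documented in source records". It gives no scoring rule for the analysis.

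Section 19.11 says: "For the primary analysis, only complete data will be used". Data are complete if the event of interest has occurred by the time point or if status is known later. The regression and hot-deck imputations that follow cover the primary endpoints only.

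In the earlier feasibility study (section 4.2): "Primary patency is lost at the first occurrence of CD-TLR, major amputation or lack of an audible signal observed".

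**The concern.** Above-ankle amputation is among the worst outcomes a treated limb can have, and it can also make the 6-month scan impossible. If such a limb is treated as missing, the estimate describes limbs that survived to be scanned, and the exclusion is informative. The plan counts the same event as failure in the primary efficacy endpoint, in limb salvage and in amputation-free survival. Patency is the one limb endpoint in the tested sequence on which the plan is silent, and there the default works in the device's favour.

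At stake is the size of the reported patency rate and, if the result falls close to the pass mark, whether the formal test succeeds.

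**Working it through.** **Inputs.** Section 19.6: the endpoint is "formally tested against a performance goal of 64"%, with "Assuming an observed 6-month patency rate of 81% and a one-sided Type I error rate of 2.5"%. The same section states that "the effective sample size given above for the primary efficacy endpoint of 175 would provide greater than 90% power", but also gives the effective sample as 186, so both sizes are used below. Table 5: freedom from above-ankle amputation in the pilot was 96.8% at 6 months, so 3.2% amputated. Amputation rates of 5% and 10% are assumptions to show a range. Counting is per subject. Every amputee is taken to lack a usable scan, so the effects shown are upper limits at each rate.

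**1. The plan's own figure.** The test passes if p̂ − 1.96·√(p̂(1−p̂)/n) > 0.64.
- n = 175: 123/175 (70.3%) has bound 63.5% and fails; 124/175 (70.9%) has bound 64.1% and passes. P(X ≥ 124 | n = 175, p = 0.81) = 99.96%.
- n = 186: the smallest pass is 132 (71.0%), with power 99.97%.

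The stated power of more than 90% reproduces.

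**2. Why the amputee leaves.** Without a qualifying scan the limb is not patent, because patency requires flow to be shown. Without a no-flow finding it is not a loss. No later status will become known, so it is not complete under section 19.11. That rule also sets a follow-up minimum for 1-year endpoints, none of which is primary, so it is not confined to the two primary endpoints.

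**3. Size.** With A amputees among N subjects and 81% patency among the N − A scanned, loss-counted patency is 0.81 × (N − A)/N.

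| N | Amputation rate | A | Loss-counted patency | Gap (points) | Power, excluded | Power, counted |
|---|---|---|---|---|---|---|
| 175 | 3.2% | 6 | 0.81 × 169/175 = 78.2% | 2.8 | 99.9% | 99.4% |
| 186 | 3.2% | 6 | 0.81 × 180/186 = 78.4% | 2.6 | 99.95% | 99.6% |
| 175 | 5% (assumed) | 9 | 0.81 × 166/175 = 76.8% | 4.2 | 99.9% | 98.2% |
| 175 | 10% (assumed) | 18 | 0.81 × 157/175 = 72.7% | 8.3 | 99.9% | 77.5% |

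**4. At the pass mark** (N = 186, A = 6).
- Excluded: 128/180 = 71.1%; 0.7111 − 1.96 × 0.0338 = 64.5%, pass.
- Counted: 128/186 = 68.8%; 0.6882 − 1.96 × 0.0340 = 62.2%, fail.

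When amputees are counted, 132 patent are needed, so the two rules disagree for 128 to 131 patent out of 180. At a true 81% among scanned subjects the probability of that range is 0.4%.

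**5. At the goal.** Suppose true loss-counted patency is exactly 64%. Patency among scanned subjects is then 0.64/(1 − a), where a is the amputation rate. With the number of amputees random, the chance of passing when they are excluded is:
- N = 175: about 9% at 3.2%, 16% at 5%, 51% at 10%; 3.4% if they are counted.
- N = 186: about 10%, 17% and 52%; 2.7% if they are counted.

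**The case against.** The best defence is that patency here means flow in a vessel, that limb loss is fully counted elsewhere, and that patency is tested only after a primary endpoint that includes amputation has been met. Adding amputation would turn an imaging measure into a composite. The 64% goal comes from 13 papers on balloon angioplasty, and the documents do not show how those papers scored amputation. If they were mainly imaging-based, a composite would be held to a benchmark built differently. This stands, and is why the imaging-only result should also be reported.

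Several stronger readings are tempting but unsupported:

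- *An amputee can have no ultrasound.* Eligible segments include the mid and distal popliteal artery and the tibioperoneal trunk, which need not be removed by an above-ankle amputation.
- *Every amputee is lost from the analysis.* A no-flow finding at the 30-day or an unscheduled scan counts as an event at or before the time point. Section 9.4 also sends to the core laboratory any duplex done around a major adverse limb event, although it does not require one before amputation.
- *Counting amputation simply repeats the pilot.* The pilot definition was post hoc, describes major amputation as above the knee, and also counted clinically driven target lesion revascularization.
- *The assumed 81% already includes amputation failures.* The pilot's 6-month figure of 80.6% is close, but section 19.6 gives no source for 81%.

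The tipping-point analysis in section 19.11 refers to the endpoint of interest and may reach patency. It would then show the worst case, but only as a sensitivity analysis.

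**Conclusion.** The concern holds in limited form. As written, the plan leaves out an amputee who has neither a qualifying scan nor an earlier no-flow finding. This raises estimated patency relative to counting a loss, by about 2.6 to 2.8 points at the pilot's amputation rate. That rate is fragile: if 3.2% represents one limb in 31 (an assumption), its exact 95% interval is about 0.1% to 17%. Higher rates give larger gaps.

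A reader might infer that the patency test is likely to give a false pass. The documents do not support that. At the planned 81%, and with 3% to 5% amputation, power is at least 98% under either scoring. The choice matters if patency is near the pass mark or amputation approaches 10%. Nor is bias against the 64% goal itself shown, since the scoring behind that goal is unknown. What is shown is an informative exclusion in the only formally tested secondary endpoint. The exclusion is inferred from the definition and section 19.11 together; no sentence states it outright.

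**What to change.** In sections 19.4, 19.8.3 and 24 (and where the definition is repeated in the synopsis and section 6.2), state that an above-ankle amputation of the target limb on or before the patency assessment is a loss of tacked-segment patency when no qualifying scan of the segment exists at the 6-month time point. Keep the subject in the denominator. Apply the same rule, descriptively, at 12 months.

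Report the imaging-only result as a sensitivity analysis, with amputees excluded or with the last scan before amputation where there is one. State in section 19.11 whether the tipping-point analysis covers patency.

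The cost is wording. No new data are needed, because these amputations are already captured as major adverse limb events. The downside is a slightly lower patency rate and a main result that is no longer purely imaging-based. The change should be made before endpoint data are available, so that the scoring is not chosen with results in view.

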#### 19.8. STATISTICAL ANALYSIS

##### 19.8.1. PRIMARY SAFETY

The primary safety endpoint of MALE+POD at 30 days will be analyzed by constructing a one-sided upper 97.5% confidence interval using the exact binomial distribution. This upper bound will be compared to the performance goal of 12%. The hypotheses being tested are:

$$H_0 : P_{MALE+POD} \geq 12\%$$

$$H_a : P_{MALE+POD} < 12\%$$

where  $P_{MALE+POD}$  is the proportion of subjects experiencing a MALE+POD event within 30 days of the procedure. All subjects that meet the ITT definition are included in this analysis.

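### Read as a plain Wald bound on subjects, the 6-month patency test runs slightly above its stated one-sided 2.5% error

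*Combined protocol and SAP*

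**What the plan says.** Section 19.6 states that 6-month patency of the tacked segment "will also be formally tested against a performance goal of 64" per cent. Its power statement begins "Assuming an observed 6-month patency rate of 81% and a one-sided Type I error rate of 2.5" per cent, and continues that "the effective sample size given above for the primary efficacy endpoint of 175 would provide greater than 90% power". The same section sets the trial's size elsewhere: "an effective sample size of 186 subjects meeting the ITT definition will be assumed", with 232 enrolled to allow for about 20% loss.

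Section 19.8.3 gives the analysis: "A one-sided lower 97.5% confidence bound will be calculated for this estimate using the standard normal approximation". It adds: "This lower bound will be compared to the performance goal of 64" per cent. It writes out no formula, names no variance and mentions no continuity correction. The estimator in that section is a proportion of tacked segments, while the parameter in the hypotheses is a proportion of subjects.

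The two primary endpoints are handled differently. Primary safety (section 19.8.1) "will be analyzed by constructing a one-sided upper 97.5% confidence interval using the exact binomial distribution". Primary efficacy (section 19.8.2) uses a continuity-corrected Z with estimated variance, and its formula is printed. Section 19.13 makes patency a formal hierarchical test, carried out only if both primary endpoints are met.

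**The concern.** A Wald lower bound takes its standard error at the observed proportion. When the goal is above 50%, any result that beats the goal has a smaller estimated variance than the goal itself. At 124/175, for example, 0.7086 × 0.2914 = 0.2065, against 0.64 × 0.36 = 0.2304 at the goal. The bound therefore sits too high and clears 64% too often when true patency is 64%.

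Patency is the only secondary endpoint with a formal hypothesis, and section 19.13 relies on the hierarchy to control type I error. If the bound does not hold 2.5%, a patency claim based on it carries more error than the plan states.

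**Working it through.** **Inputs.** Goal 64%, one-sided error 2.5% and assumed patency 81% (section 19.6). Sample sizes 175 and 186 (section 19.6) and the enrollment maximum of 232 (sections 7.1 and 19.6). The span 150 to 232 is an assumption covering the attainable numbers of evaluable subjects. The unit is the subject. Segments are treated at step 6.

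**1. The plan's own figure.** With n = 175 and the null variance in the critical value, power is

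Φ{[0.81 − 0.64 − 1.96 × √(0.64 × 0.36/175)] / √(0.81 × 0.19/175)} = Φ{(0.17 − 0.0711)/0.0297} = 99.96%.

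The exact binomial power of the Wald rule is also 99.96%. The plan's claim of more than 90% reproduces.

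**2. The Wald cut-off.** Success requires p̂ − 1.96 × √(p̂(1 − p̂)/n) > 0.64. At n = 175:
- 123 patent: 0.7029 − 1.96 × 0.03455 = 0.635, fail.
- 124 patent: 0.7086 − 1.96 × 0.03435 = 0.641, pass.

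**3. Exact error.** This is P(X ≥ cut-off) for X binomial (n, 0.64). The exact rule takes the smallest count whose tail probability is at most 2.5%, which is the Clopper-Pearson bound.

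| n | Wald cut-off | Wald error | Exact cut-off | Exact error | Exact-rule power at 81% |
|---|---|---|---|---|---|
| 175 | 124 | 3.36% | 125 | 2.31% | 99.92% |
| 186 | 132 | 2.71% | 133 | 1.86% | 99.94% |
| 232 | 163 | 2.63% | 164 | 1.88% | 99.99% |

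**4. All 83 values of n from 150 to 232.**
- Wald: above 2.5% at all 83. Minimum 2.5004% (n = 202), maximum 3.64% (n = 159), mean 2.99%.
- Score (variance at 64%): above 2.5% at 30 of 83, including 186 and 232. Maximum 2.84%, mean 2.37%.
- Exact: never above 2.5%. Range 1.66% to 2.48%, mean 2.07%. Power at 81% is at least 99.65%.

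A continuity correction like the one in section 19.8.2 would not be enough. Over n = 140 to 232, the corrected Wald rule still exceeds 2.5% at 53 of 93 values (maximum 3.08%).

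**5. Effect on the decision.** The Wald and exact cut-offs differ by exactly one subject at every n from 150 to 232, so the two rules disagree only when the count equals the Wald cut-off. At a true patency of 81% that probability is 0.04% at n = 175 and 0.03% at n = 186. At a true 75% it is about 3% at either size.

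**6. The unit.** Suppose, as an assumption, 166 subjects with two tacked segments each, so n = 332 segments, with the Wald rule applied to segments. The error at 64% is 2.48% if segments are independent. With a within-subject correlation of 0.01, 0.2 or 0.5 it is 2.54%, 3.66% or 5.47%.

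**The case against.** The section openly calls its method an approximation, and it is a common one. The mean excess over 2.5% is 0.49 points (2.99 − 2.50) and is practically nil at n = 202. The exact rule misses in the other direction by a similar amount (2.50 − 2.07 = 0.43 points), so someone content with an approximately nominal error could reasonably prefer a score bound. All of this stands, and it limits the severity. It does not make the stated 2.5% correct.

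A reader might infer that the error exceeds 2.5% at every plausible sample size, without conditions. The documents do not support that. Section 19.8.3 names no variance, and under a score variance most sample sizes stay within 2.5%. It also leaves the unit open: with independent segments counted, the Wald error first falls below 2.5% at n = 299. The statement holds only for the Wald variance and subject-level n up to 232.

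A reader might also infer that trial success is compromised. It is not: section 19.12 defines success by the two primary endpoints alone, and patency is tested only after both are met.

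Finally, patency is not the only test here with an estimated variance. The continuity-corrected Z for primary efficacy, enumerated the same way at 74%, has an exact error of 3.21% at n = 186. That shows the behavior is not peculiar to patency. It does not excuse it there.

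**Conclusion.** The concern holds in a limited form. With a plain Wald bound on subjects, the patency test does not hold its stated one-sided 2.5% at any n from 150 to 232. The excess averages about half a point and is at most 1.14 points (3.64 − 2.50).

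This rests on two readings: estimated variance, which is natural for a bound placed on an estimate but is not stated, and the subject as unit, which is how the hypothesis is worded. The plan's power claim is unaffected, and at the assumed 81% the verdict would almost never change. The conflict between segments and subjects in the same section is the larger threat to the error rate, because correlated segments can push it well beyond the Wald excess. Low severity.

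**What to change.** In section 19.8.3, replace the normal-approximation bound with the exact binomial (Clopper-Pearson) one-sided lower 97.5% bound. State that it is computed on subjects, the unit in the hypothesis, and not on tacked segments. The text should also say how a subject with several tacked segments is counted.

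The cost is a sentence or two of text. One more patent subject is needed for success, the reported lower bound is slightly lower, and the test becomes mildly conservative. At n = 175, power at 81% goes from 99.96% to 99.92%.
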